#### **4.2.7. Discontinuations and Loss to Follow-up**

Each treated patient from this study receives study medication as a single IA injection. Therefore, discontinuation from treatment is not applicable.

Each patient may only discontinue from the study for further assessments and study visits. Data collected from discontinued patients will be included in the CSR. Patients who discontinue from the study may be replaced at the discretion of the sponsor. Version 3.0 of the protocol separated the study into two parts as the study was put on-hold to new recruitment for an extended period to investigate six patients that did not receive complete study drug administration. All patients enrolled up to the time that the amendment was implemented at each site were followed for at least 12 weeks or up to the time of this amendment, when they were discontinued from the study.

#### **4.2.8. Missing, Unused, and Spurious Data**

Missing values will not be imputed and data will be analyzed “as observed”.

For WOMAC, the rules as described in the WOMAC user guide (Bellamy 2011) will be used. Specifically, if at least 2 pain, both stiffness, or at least 4 function items are missing, the patient's response will be regarded as invalid and the score for that given subscale as well as the total score will be left missing. If no more than 1 pain, 1 stiffness, and less than 4 function items are missing, the missing value in a given subscale will be imputed using the average of all items in the given subscale. Imputed WOMAC scores will be flagged in the data listings.

For the HOOS-QOL subscale, the rules as described in HOOS Scoring 2013 (<http://www.koos.nu/>) will be used. Specifically, the score is only calculated if 50% items (2 out of 4) are non-missing. Otherwise the score will be set to missing.

#### **4.2.9. Visit Windows**

Data collected at unscheduled visits will be mapped to the closest scheduled visit, but only if that data is not already available in that visit. Otherwise data will be summarized and presented according to the nominal visit as recorded on the Case Report Form (CRF).

#### **4.2.10. Baseline definitions**

Baseline is the Baseline/Day 1 assessment prior to administration of the first dose of study treatment. If the Baseline result is missing, the last non-missing result prior to administration of study treatment may be used from the screening period.

### **4.3. Interim Analyses**

There will be no interim analyses for Part I of this study.

### **4.4. Final Analyses**

The analyses of the Part I data will be performed in an unblinded manner when all Part I patients have completed, withdrawn or discontinued from the study. Only data from Part I of the

---

study will be presented. Final analyses specified in the protocol and SAP will be completed and reported in the CSR.

Post-hoc, exploratory analyses, may be completed to further understand and elucidate study results. Any post-hoc, exploratory, analyses completed will be clearly identified as such in the final CSR.

#### **4.5. Patient Disposition**

All patients who are randomized will be accounted for in this study.

Patient disposition will be tabulated and include the total number of patients randomized, treated, completed and early terminated, reason for early termination and the number in each patient population.

The following by-patient data listings will be presented:

- Study completion information including the reason for premature study discontinuation, if applicable.
- Inclusion/exclusion criteria not met.
- Patient inclusion in each of the analysis populations (FAS, SP).

#### **4.6. Protocol Deviations**

The number and percentage of patients with at least one protocol deviation will be summarized for the SP. Additionally, incidence by type of deviation will be presented; in these tabulations patients could be counted in more than one category if they have a deviation attributed to multiple categories. All protocol deviations will be presented in a data listing.

#### **4.7. Demographic and Baseline Characteristics**

Demographic and Baseline characteristics will be summarized for the SP.

No formal statistical comparisons will be performed.

All collected demographic, Baseline characteristic, and medical history data will be provided in data listings.

##### **4.7.1. Demographic Characteristics**

The following Baseline parameters will be summarized for the SP:

- Age (year) at consent - Age will be calculated as the years between date of birth and date of informed consent, and will be rounded down to the nearest year.
- Weight (kilogram (kg));
- Height (centimeter (cm));
- Gender (Male/Female);

- 
- Body mass index (BMI) (kg/meter (m));
  - BMI category:
    - Underweight: <18.5 kg/m^2
    - Normal: 18.5 to <25.0 kg/m^2
    - Overweight: 25.0 to <30.0 kg/m^2
    - Obesity Class I: 30.0 to <35.0 kg/m^2
    - Obesity Class II: 35.0 to <40.0 kg/m^2
    - Obesity Class III: >=40.0 kg/m^2
  - Ethnicity (Hispanic or Latino / Not Hispanic or Latino);
  - Race (White / Asian / Black or African American / American Indian or Alaska Native / Native Hawaiian or Other Pacific Islander);

Age, height, weight, and BMI will be summarized using descriptive statistics (number of patients, mean, SD, median, minimum, and maximum). The number and percentage of patients in each gender, ethnicity, race and BMI category will also be presented.

WOMAC A (pain) average of Screening 2 and Day 1, which was used as a stratification factor in randomization, will be presented in the following classifications: 5 to < 6, 6 to < 7, and  $\geq$  7 to 9.

Patient questionnaires for Baseline PD-Q, PHQ-9, GAD-7, PCS, and ISI will be presented in data listings.

#### **4.7.2. OA Medical History**

OA history and index hip characteristics as collected on the CRF will be summarized for the SP.

Time from primary diagnosis of OA in the index hip to Day 1 of the study in days (first dose date – date of diagnosis + 1), will be computed and presented descriptively. If only month and year of initial diagnosis is available, day will be imputed as 1 for calculations. If month and day are missing, the time from primary diagnosis will be computed as year of first dose minus year of diagnosis. If year is missing, time from diagnosis will not be computed.

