7.9.3. Review of Eligibility, Medical History, Prior Treatment and Medications

Eligibility criteria (inclusion and exclusion criteria), medical history (including OA history), prior treatment and medications are reviewed during Screening and at Day 1 per the schedule noted in Table 7-2.

OA medical history includes ACR diagnosis details, OA diagnosis date (if available), number of days with index hip pain in the last month, previous IA steroid, PRP or hyaluronic injections, presence of OA in other joints, prior procedures or surgeries for index hip OA.

At Day 1, eligibility should be confirmed (inclusion/exclusion criteria review against any new information/findings through Day 1 assessment).

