## 4. STATISTICAL METHODS

### 4.1. Sample Size Justification

Approximately 70 patients will be randomized in Part I and approximately 440 patients will be randomized in Part II in this study (an estimated 35 and 220 per treatment group, respectively.)

For Part I, a sample size of approximately 35 per arm will provide information regarding the treatment effect. For Part II of the study, the expected sample size was determined based on the primary endpoint as follows. A minimum sample size of N=212 per arm for the placebo and the FX006 group has 90% power to yield a statistically significant difference (alpha=0.05, 2-sided) if the true underlying difference at Week 12 is 0.65 and with an assumption of 2.0 for the standard deviation (SD). For the first key secondary endpoint, the sample size of N=220 per treatment group has 90% power to yield a statistically significant difference between FX006 and placebo if the true underlying difference is 0.68 at Week 12, assuming a SD of 2.125. An early discontinuation rate of 6% was assumed. The data from Part I may be used to inform if the above assumptions were appropriate and the planned sample size for Part II should remain at 440, or whether a smaller sample size would be feasible.

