## 7. CLINICAL STUDY REPORT APPENDICES

### 7.1. Statistical Tables and Figures to be Generated

Table 14.1.1	Patient Enrollment and Disposition
Table 14.1.2	Demographic and Baseline Characteristics (Safety Population)
Table 14.1.3	Osteoarthritis History and Index Hip Characteristics (Safety Population)
Table 14.1.4	Summary of Major Protocol Deviations (Safety Population)
Table 14.1.5	Study Drug Exposure Summary (Safety Population)
Table 14.2.1.1	Analysis of WOMAC A Pain Subscale (Full Analysis Set)
Figure 14.2.1.1	LS Mean Change from Baseline (+/- SE) in WOMAC A Pain Subscale Over Time (Full Analysis Set)
Table 14.2.1.1.1	Analysis of WOMAC A Pain Subscale, Patients with Baseline WOMAC A Pain Score 5 to <6 (Full Analysis Set)
Table 14.2.1.1.2	Analysis of WOMAC A Pain Subscale, Patients with Baseline WOMAC A Pain Score 6 to <7 (Full Analysis Set)
Table 14.2.1.1.3	Analysis of WOMAC A Pain Subscale, Patients with Baseline WOMAC A Pain Score $\geq 7$ to 9 (Full Analysis Set)
Figure 14.2.1.1.1	LS Mean Change from Baseline (+/- SE) in WOMAC A Pain Subscale Over Time by Baseline WOMAC A Pain Score (Full Analysis Set)
Table 14.2.1.1.2.1	Analysis of WOMAC A Pain Subscale, Patients with Unilateral Hip OA (Full Analysis Set)
Table 14.2.1.1.2.2	Analysis of WOMAC A Pain Subscale, Patients with Bilateral Hip OA (Full Analysis Set)
Figure 14.2.1.1.2	LS Mean Change from Baseline (+/- SE) in WOMAC A Pain Subscale Over Time by Unilateral/Bilateral Hip OA (Full Analysis Set)
Table 14.2.1.2	Analysis of WOMAC B Stiffness Subscale (Full Analysis Set)
Figure 14.2.1.2	LS Mean Change from Baseline (+/- SE) in WOMAC B Stiffness Subscale Over Time (Full Analysis Set)
Table 14.2.1.2.1.1	Analysis of WOMAC B Stiffness Subscale, Patients with Baseline WOMAC A Pain Score 5 to <6 (Full Analysis Set)

---

Table 14.2.1.2.1.2	Analysis of WOMAC B Stiffness Subscale, Patients with Baseline WOMAC A Pain Score 6 to <7 (Full Analysis Set)
Table 14.2.1.2.1.3	Analysis of WOMAC B Stiffness Subscale, Patients with Baseline WOMAC A Pain Score $\geq 7$ to 9 (Full Analysis Set)
Figure 14.2.1.2.1	LS Mean Change from Baseline (+/- SE) in WOMAC B Stiffness Subscale Over Time by Baseline WOMAC A Pain Score (Full Analysis Set)
Table 14.2.1.2.2.1	Analysis of WOMAC B Stiffness Subscale, Patients with Unilateral Hip OA (Full Analysis Set)
Table 14.2.1.2.2.2	Analysis of WOMAC B Stiffness Subscale, Patients with Bilateral Hip OA (Full Analysis Set)

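### Time since hip OA diagnosis is defined in days, but the year-only rule in SAP 4.7.2 gives an unconverted number of years

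*SAP*

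**What the plan says.** SAP 4.7.2 (OA Medical History) sets out one variable and a rule for each level of completeness of the diagnosis date:

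- Complete date: "Time from primary diagnosis of OA in the index hip to Day 1 of the study in days (first dose date – date of diagnosis + 1".
- Month and year only: "If only month and year of initial diagnosis is available, day will be imputed as 1 for calculations". The result stays in days.
- Year only: "If month and day are missing, the time from primary diagnosis will be computed as year of first dose minus year of diagnosis".
- Year missing: "If year is missing, time from diagnosis will not be computed".

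The variable is to be presented descriptively with the OA history of the Safety Population. The matching output is Table 14.1.3, "Osteoarthritis History and Index Hip Characteristics (Safety Population". Under SAP 4.2.1, a continuous variable is summarised by n, mean, median, SD, minimum and maximum. Protocol 7.9.3 lists the item as "OA diagnosis date (if available" followed by a closing bracket, so a date need not be on record for every patient.

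**The concern.** The first two rules give days and the third gives years, and all three feed the same summary. The SAP gives no multiplier, separate variable, separate row or footnote for the year-only patients. The list of changes in SAP section 5 does not mention the matter.

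At stake is the description of disease duration in the enrolled patients. SAP 1.2 says its summaries will support the Part I results of the clinical study report, as well as regulatory filings and manuscripts. A row that mixes values in the thousands with values in single digits would misdescribe the population in those documents.

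**Working it through.** The plan states no numerical result for this variable, so there is no figure to reproduce. The check applies the rules of SAP 4.7.2 as written.

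**Step 1: one patient.** Assumed for illustration: first dose F on 15 March 2019 and a diagnosis in 2014. With diagnosis date X, the days formula is F − X + 1.

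| What is known of the diagnosis date | Calculation | Value |
|---|---|---|
| 15 March 2014 | F − X + 1 | 1,827 |
| March 2014 | X set to 1 March 2014, same formula | 1,841 |
| 2014 | 2019 − 2014 | 5 |
| 2019 (same calendar year as dosing) | 2019 − 2019 | 0 |

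For any diagnosis date in 2014 the days formula lies between 1,536 (31 December) and 1,900 (1 January), so the year-only value of 5 cannot be a number of days. Converted, it is 5 × 365.25 = 1,826.25, and the understatement is a factor of 365.25. The value 0 is also outside the range of the days formula, which gives at least 1 for a diagnosis on or before Day 1.

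**Step 2: the summary row.** Assumptions: all patients have a five-year history (1,826.25 days), and a share q of dates is year-only. Part I size is from SAP 4.1: "Approximately 70 patients will be randomized in Part I".

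- Mean = (1 − q) × 1,826.25 + q × 5
- SD (divisor n) = √(q(1 − q)) × (1,826.25 − 5)

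| q | Patients of 70 | Reported mean | Shortfall in mean | Reported SD (true SD 0) | Reported median |
|---|---|---|---|---|---|
| 0.1 | 7 | 1,644 | 10% | 546.4 | 1,826 |
| 0.2 | 14 | 1,462 | 20% | 728.5 | 1,826 |
| 0.3 | 21 | 1,280 | 30% | 834.6 | 1,826 |
| 0.5 | 35 | 916 | 50% | 910.6 | 916 (midpoint of 5 and 1,826.25) |

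The reported minimum is 5 in every row of the table.

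**Step 3: the median when durations vary.** In the uniform example the median holds until half the dates are year-only. With a spread of durations it can move sooner. Suppose q = 0.2, every year-only value falls below all the others, and having a year-only date is unrelated to duration. The reported median is then the (0.5 − 0.2)/0.8 = 0.375 quantile of the correctly computed values.

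**The case against.** The strongest reply is that the SAP never says the year difference is to be labelled or pooled as days. A competent programmer would convert it, or would notice a 5 among values in the thousands. That may well happen. But the text does not ask for a conversion, and the month-and-year rule in the same paragraph takes care to keep the result in days. A pre-specified derivation should not depend on an unrecorded correction.

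The second reply is that year-only dates may be few or absent. This stands. The protocol wording shows only that a date may be unavailable. The better evidence that year-only dates were foreseen is that the SAP has a rule for them. Their number is not given, so every size above is conditional.

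Three stronger readings are tempting and are not supported:

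- **That the mean, median and minimum will all be wrong.** This needs year-only dates to occur. Even then the median does not move in the uniform example at 10%, 20% or 30%, and the minimum changes only if no correctly computed value is lower.
- **That the arms will look unbalanced.** This needs year-only dates to fall unevenly between randomised arms, and nothing in the documents suggests that they do. SAP 4.7 plans no formal baseline comparison.
- **That efficacy results are affected.** The variable is not among the model covariates (SAP 4.2.4) or the planned subgroups (SAP 4.2.6), and Part I is exploratory (SAP 4.2.5).

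The collected medical history also goes into data listings (SAP 4.7; Listing 16.2.4.3), so a reader could trace an odd value to its source.

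**Conclusion.** The rule is wrong as written. It puts years and days into one summary with no conversion. For each patient with a year-only date and a diagnosis in an earlier calendar year, the literal value is too small by a factor of roughly 365, and for a diagnosis in the year of dosing it is 0. If such dates occur, the mean is understated, the minimum can be false and the SD is distorted. Whether the median shifts depends on the spread of durations and the share of year-only dates.

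The means of 1,462, 1,280 and 916 at shares of 20%, 30% and 50% rest on an assumed uniform five-year history and on assumed shares. The unit error itself rests on neither assumption. The consequence is confined to one descriptive baseline row and any listing of the derived value. No efficacy or safety conclusion depends on it, so this is a minor correction.

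**What to change.** Replace the year-only sentence in SAP 4.7.2 with a rule that imputes a month and day and then uses the existing days formula. For example, impute 1 July of the diagnosis year, or 1 January if 1 July falls after first dose.

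For the illustrative patient, 1 July 2014 is 108 days after 15 March 2014, so the value is 1,827 − 108 = 1,719 days, inside the possible range of 1,536 to 1,900. For a 2019 diagnosis the fallback to 1 January 2019 gives 73 + 1 = 74 days, so the zero disappears. Imputing 1 January throughout would match the SAP's first-of-the-month convention, but it always gives the longest duration the year allows. Multiplying the year difference by 365.25 restores the unit but still gives 0 for a same-year diagnosis.

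Reporting the whole variable in years is optional. It would require dividing the full-date and month-and-year values by 365.25 as well, with the unit stated in the table.

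The cost is one SAP sentence and one line of derivation code, with no new data. Protocol 9.1 says Parts I and II will be analysed in the same manner under separate SAPs, so the wording should be checked if it is reused for Part II.

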#### **4.7.3. Prior medication**

All prior medications will be presented in the concomitant medication data listing with a flag identifying which medications are prior medications (refer to [Section 4.11.5](#) for details on defining prior and concomitant medications).

### **4.8. Patient Randomization**

Patient Randomization information will be provided in a listing, with assigned treatment, patient ID, date of informed consent, randomization date, dose date, completed study, study completion date, reason for early termination.

---

## 4.9. Study Drug Exposure

Details of study drug administration will be summarized for the SP.

The position of hip during injection, approach during injection, the numbing agent used, whether or not fluoroscopy guidance was used, volume of synovial fluid aspirated, whether a 20 gauge, 3 1/2" or 6" needle, was used, whether entire contents of the syringe were injected, reason (if entire contents not injected), and volume remaining in syringe will be presented.

All study drug exposure data will be presented in a data listing.

## 4.10. Efficacy Evaluation

All efficacy analyses will be conducted using the FAS.

In addition to the analyses described below, subgroup analyses will be performed as described in [Section 4.2.6](#).

### 4.10.1. WOMAC

The following WOMAC scales/questions will be analyzed:

- WOMAC A (pain subscale)
- WOMAC B (stiffness subscale)
- WOMAC C (function subscale)
- WOMAC (total)

Since randomization is stratified by WOMAC A (pain) average of Screening 2 and Day 1 scores of 5 to <6, 6 to <7, and  $\geq 7$  to 9, this value will be provided in the data listing.

#### 4.10.1.1. Change from Baseline

For the WOMAC subscales, scores at each assessment time point (Baseline, Week 1, Week 4, Week 8, Week 12, etc.) will be calculated as the average of the responses to all questions in the subscale. Total score will be computed as the average of the average responses on each of the subscales (e.g. Average A + Average B + Average C divided by 3). This will provide a uniform scoring of 0 to 10 for each subscale and easier interpretation. Imputation rules are as presented in [Section 4.2.8](#).

Each of the WOMAC subscales will be analyzed separately using a longitudinal MMRM with fixed effects for Baseline score for the endpoint, treatment group, study week, treatment-by-week interaction, study site, and Baseline WOMAC A score. The analysis will include all study weeks of data, and not be confined to only that at Baseline and Week 12. Subject will be the random effect. Treatment differences from placebo will be estimated via least squares (LS) means from the analysis model along with 95% CIs, and associated 2-sided p-values. This model assumes missing at random and includes only observed data.

This model will be run using the SAS/STAT PROC MIXED procedure with an unstructured correlation matrix to model the within-subject errors. If the unstructured covariance matrix does not converge when fitting the mixed model, further investigation into the most appropriate correlation matrix will be conducted. The final selection of the correlation matrix to be used in fitting the mixed model will be presented in the table output and fully documented in the results section of the CSR.

Sample SAS code that can be used to implement the mixed analysis is provided below:

```
proc mixed data= dsin1 method=reml;
  class subjid armcd avisitn site;
  model chg = base armcd avisitn armcd*avisitn site base_womaca;
  repeated avisitn /type=un subject=subjid;
  lsmeans armcd/diff=control ('0') cl;
  /*[where 0 represents treatment=placebo]*/
  lsmeans armcd*avisitn /pdiff cl;
run;
```

Descriptive statistics will also be presented and will include number of observations, unadjusted mean, SD, median, minimum and maximum. Change from Baseline will also be presented. For the change from Baseline calculation, Baseline is the WOMAC result obtained on Day 1 prior to first dose. The adjusted change from Baseline will also be presented using results from the MMRM.

A line plot presenting LS means change from Baseline over time will be produced. Each treatment group will be plotted on a separate line with SE bars. Jitter will be used as needed to distinguish overlapping data.

#### 4.10.1.2. AUE for Change from Baseline in WOMAC over Time

AUE for change from Baseline in WOMAC A and C over various time intervals will be examined.

AUE will be calculated for the subjects who have assessments in all available visits, from a linear trapezoidal rule using the following formula for change from Baseline in WOMAC A and WOMAC C:

$$AUE_{t_i-t_{i+n}} = \sum_{t_i}^{t_{i+n}} ((WD_i + WD_{i+1})/2) * (t_{i+1} - t_i)$$

Where  $WD_i$  = WOMAC difference (change) from Baseline in WOMAC score for time  $t_i$ , and  $WD_{i+1}$  = WOMAC difference (change) from Baseline in WOMAC score for time  $t_{i+1}$ , over the time interval  $t_i$  to  $t_{i+1}$ . Only non-missing time intervals will be part of the sum for each AUE calculation (Farrar et al. 2000). If a patient does not have a value for the last visit in a time interval, that patient will be excluded from the AUE analysis for that time interval. For example, if a patient has missing data for Week 12, AUEWeek 1 to Week 12 will not be calculated.

---

The following AUE endpoints will be computed for each subject in the study over the sampling intervals:

- AUEWeek 1 to Week 4
- AUEWeek 1 to Week 8
- AUEWeek 1 to Week 12

The comparisons the AUE endpoints will be estimated from an ANCOVA with model parameters for treatment and covariates of Baseline score of the AUE endpoint, WOMAC A score and study site. All models will include Baseline WOMAC A score as a covariate, regardless of the AUE endpoint, since randomization was stratified by WOMAC A scores.

Descriptive statistics will include the LS means and standard error, 95% CI, LS mean difference from placebo, and 2-sided p-value relative to placebo.

Sample SAS code that can be used to implement the AUE analysis is provided below:

```
proc mixed data= dsin1;
  class armcd site;
  model aueval = base armcd site base_womaca;
  lsmeans armcd/diff=control ('0') cl;
  /*[where 0 represents treatment=placebo]*/
  ods output lsmeans = lsm diffss = diffss;
run;
```

All AUE data will be presented in a data listing.

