9.4.3. Efficacy Analyses

Primary Efficacy Analysis

The primary endpoint will be analyzed with a longitudinal mixed model for repeated measures (MMRM) with fixed effects for treatment group, study week, treatment-by-week interaction and Baseline score. Subject will be the random effect. Treatment differences from control will be estimated via least square means from the analysis model along with 95% confidence intervals, and associated 2-sided p-values. This model assumes missing at random and includes only observed data.

Secondary Efficacy Analyses

Key secondary endpoints will be assessed similarly to the primary endpoint. Multiplicity will be addressed by analyzing the key secondary endpoints sequentially in the order presented in the protocol, testing each endpoint at the nominal alpha=0.05, 2-sided level to ensure overall type I error control at the 2-sided 0.05 level.

Additional continuous secondary efficacy endpoints will also be assessed similarly to the primary endpoint, but are not part of the sequential testing approach. Categorical end points will be compared via chi-square or exact tests depending on incidence rates.

AUE will be calculated and comparisons of the AUE endpoints will be estimated from an Analysis of Covariance (ANCOVA) with model parameters for treatment and covariates of Baseline WOMAC A score and study site. Full details of the AUE analyses will be detailed in the SAP.

Efficacy Analyses For The Open-Label Extension Phase (Part II)

Exploratory efficacy endpoints for the open-label extension phase will be analyzed similarly to the primary and secondary endpoints, but separately for the time period prior to the second injection and the time period post the second injection. Time-to-event endpoints will be assessed via log-rank tests and results will be presented in Kaplan-Meier plots.

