## 2. STUDY DESIGN

### 2.1. Synopsis of Study Design and Randomization Methodology

This is a two-part, multi-center, randomized, double-blind, placebo-controlled, parallel-group study in patients with hip OA. Approximately 70 patients will be enrolled in Part I and approximately 440 patients will be enrolled in Part II of the study. In each part, patients will be randomized to one of two treatment groups (1:1) and treated with a single IA injection of either 32 mg FX006 or normal saline.

Eligible patients will be randomized within strata defined by Baseline Western Ontario and McMaster Universities Osteoarthritis Index (WOMAC) A (pain) (0-10 numeric ratings scale (NRS)) average of Screening 2 and Day 1 with the following classifications: 5.0 to < 6.0, 6.0 to < 7.0, and ≥ 7.0 to 9.0.

FX006 or saline placebo will be administered as a single IA injection with a 12-week follow-up period in the double-blind phase.

Patients participating in Part I of the study will be treated with a single IA injection of either 32 mg FX006 or normal saline and will return for follow up visits at Weeks 12, 16, 20, and 24 or up until implementation of Protocol Version 3.0. The patients will be discontinued at the time of notification by the Investigator.

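### The completers-only rule drops any patient without Week 12 from the Weeks 1-12 AUE; a weighted contrast from the planned MMRM would keep them under the SAP's own missing-at-random assumption

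*SAP*

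**What the plan says.** Protocol 9.4.3 sets the method for the AUE endpoints: "AUE will be calculated and comparisons of the AUE endpoints will be estimated from an Analysis of Covariance (ANCOVA"). It leaves the details to the SAP. SAP 4.10.1.2 computes a trapezoidal AUE of change from baseline in WOMAC A and C for Weeks 1-4, 1-8 and 1-12. For a patient without the final visit of an interval, "that patient will be excluded from the AUE analysis for that time interval"; the SAP's own example is Week 12 missing, so no Weeks 1-12 AUE. The covariates are the baseline score of the endpoint, baseline WOMAC A and site.

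For patients with a gap before the final visit, the section says two things. It limits the AUE to patients assessed at every visit, and it also says that intervals with missing data are simply left out of the sum.

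SAP 4.10.1.1 analyses the same WOMAC scores with an MMRM that uses all study weeks, treatment-by-week terms and an unstructured matrix: "This model assumes missing at random and includes only observed data". SAP 4.10.9 makes missing-data sensitivity analyses optional and names no method. AUE is an additional secondary endpoint, and SAP 2.4 makes every Part I endpoint exploratory.

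**The concern.** Two analyses of the same scores rest on different missing-data assumptions. The MMRM allows dropout to depend on pain already recorded. The AUE ANCOVA conditions only on baseline variables and site, so it needs Week 12 completion to be unrelated to post-baseline pain once those are accounted for. It also leaves out Week 1, 4 and 8 scores that bear directly on the quantity being estimated. If patients leave because of poor relief, and more do so in one arm, the AUE difference and the weekly MMRM differences can disagree for a purely technical reason.

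The gap rules raise a second problem. If missing intervals are left out of the sum, a patient with an incomplete curve gets an AUE closer to zero than the same pain course would give with full data.

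**Working it through.** **1. The plan's own figures.** SAP 2.1: "patients will be randomized to one of two treatment groups (1:1"). SAP 4.1: the design "has 90% power to yield a statistically significant difference (alpha=0.05, 2-sided"); for WOMAC A it takes a Week 12 difference of 0.65 and an SD of 2.0. With n per arm = 2(z0.975 + z0.90)²SD²/difference²:

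- WOMAC A: 2 × 10.507 × 2.0²/0.65² = 198.96, so 199. "An early discontinuation rate of 6% was assumed": 199/0.94 = 211.7, so 212, as stated.
- First key secondary, "if the true underlying difference is 0.68 at Week 12, assuming a SD of 2.125": 2 × 10.507 × 2.125²/0.68² = 205.2, so 206; 206/0.94 = 219.1, so 220, as stated.

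Both reproduce. The plan gives no figure for AUE.

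**2. AUE as a contrast.** The visits are Weeks 1, 4, 8 and 12, so the intervals last 3, 4 and 4 weeks:

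(3/2)(W1 + W4) + (4/2)(W4 + W8) + (4/2)(W8 + W12) = 1.5 W1 + 3.5 W4 + 4 W8 + 2 W12.

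The weights sum to 11. A patient who leaves after Week 8 has supplied 1.5 + 3.5 + 4 = 9 of them. For Weeks 1-8 the weights are 1.5, 3.5, 2; for Weeks 1-4 they are 1.5, 1.5.

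**3. Patients affected.** At 6%, 0.06 × 70 = 4.2 Part I patients lose the Weeks 1-12 AUE. At 15% it is 10.5 and at 25% it is 17.5. The last two rates are illustrative.

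**4. Bias.** SD 2.0 and the difference of 0.65 come from SAP 4.1. Not in the documents, and assumed here: the difference of 0.65 holds at every visit (true AUE difference -0.65 × 11 = -7.15); correlation between visits is 0.6; dropout log-odds rise 0.8 per pain point where loss depends on pain; there are no site effects. Simulations used 500,000 to 1,000,000 patients per arm.

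| Loss by Week 12 | Placebo / FX006 | Last-visit rule | MMRM contrast |
|---|---|---|---|
| Unrelated to pain | 6% / 6% | 0% | 0% |
| Depends on last score, same rule in both arms | 7.3% / 4.8% | 7% shrinkage | 0% |
| Poor responders, placebo only | 6% / 0% | 19% shrinkage | 0% |
| Poor responders, FX006 only | 0% / 6% | 19% inflation | 0% |
| Poor responders, equal rates | 6% / 6% | about 0% | 0% |
| Depends on the unseen score (MNAR), same rule | 7.3% / 4.7% | 7% shrinkage | 2.5% shrinkage |

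Equal rates alone do not protect. With 6% lost in each arm, but poor responders leaving placebo and good responders leaving FX006, the last-visit rule shrank the effect by 37% and the contrast by 0%. With pain-related loss in placebo (8.5%) and unrelated loss in FX006 (3.2%), the figures were 25% and 0%. When that placebo loss depended on the unseen score, they were 26% and 9%. An AR(1) correlation of 0.7, run for the unrelated-loss and same-rule settings and for the settings in this paragraph, gave nearly the same results.

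**5. Size against the standard error.** With 35 per arm and 6% unrelated loss, the simulated standard error is 4.46 for the last-visit rule and 4.37 for the contrast, a ratio of 1.02. A separate run at 32 per arm gave about 3%. At 15% loss the values are 4.77 and 4.49; at 25%, 5.12 and 4.56.

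- A 7% bias is 0.07 × 7.15 = 0.50 units, or 0.50/4.46 = 0.11 standard errors.
- A 19% bias is 1.36 units, or 0.30 standard errors.
- Scaled to 220 per arm, the standard error is 4.46 × √(35/220) = 1.78, and the same biases are 0.28 and 0.76 standard errors.

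**6. Gaps with Week 12 present.** Summing only the complete intervals covers 8 of 11 weeks if Week 1 is missing, 4 of 11 if Week 4 is missing, and 3 of 11 if Week 8 is missing. A patient with a constant change d and no Week 8 score would be given 3d instead of 11d.

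**The case against.** The strongest reply is that this matters little where the SAP applies. Part I is exploratory with no multiplicity control, AUE lies outside the testing sequence, and the bias is at most about 0.3 standard errors in the 6% scenarios that give the 7-19% range. The observed scores are not lost to the study: they enter the weekly MMRM, and a patient who leaves after Week 8 stays in the Weeks 1-4 and 1-8 AUEs. Some Part I patients may lack Week 12 because the sponsor ended follow-up (SAP 4.2.7), which is plausibly unrelated to pain; the cost is then precision only. The documents do not say how many stopped before Week 12. All of this stands and limits the weight of the point.

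It also stands that Part II will have its own SAP. Protocol 9.4.3 contains no last-visit rule, so nothing shows that Part II will use it. But Protocol 9.4 says that both parts will be analysed in the same manner, which makes this the natural template.

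A reader might infer from the printed summation limit that the Weeks 1-12 AUE would include Weeks 12-16. The section names the end of each interval and treats Week 12 as the last visit of Weeks 1-12, so this is a slip of notation only.

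**Conclusion.** The point holds as a low-severity improvement. The last-visit rule leaves out patients whose recorded scores carry most of the Weeks 1-12 weight, and it rests on a stricter missing-data assumption than the SAP makes for the same scores. At 6% loss the bias was 7% to 19% shrinkage, or 19% inflation, and about zero when loss was equal in rate and in its dependence on pain. The mixed mechanisms in the working gave more. These sizes rest on the assumed effect profile, correlation and dropout slope.

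Two stronger readings are tempting and not supported. The first is that the rule always pulls the result toward no difference: the sign depends on which arm loses which patients, and the documents give no loss by arm. The second is that the MMRM contrast removes the bias outright. It does so under missing at random with a correctly specified model. Under MNAR about a third of the bias remained in these runs. Nor can the contrast recover patients left out of the full-dose FAS; SAP Section 5 cites six incomplete administrations.

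The conflict between the two gap rules is a separate defect of the text and needs no assumption.

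**What to change.** In SAP 4.10.1.2, estimate each AUE difference as an explicit contrast of the treatment-by-week LS means from the MMRM in 4.10.1.1:

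- Weeks 1-4: 1.5, 1.5
- Weeks 1-8: 1.5, 3.5, 2
- Weeks 1-12: 1.5, 3.5, 4, 2

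Use one ESTIMATE or LSMESTIMATE statement per interval, with zero coefficients for any visit outside the interval, including those after Week 12. The overall treatment LS mean in the sample code is no substitute, because it weights all visits in the data equally. State that the estimate is valid under missing at random, and name one MNAR sensitivity analysis in 4.10.9, for example delta-adjusted.

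Keep the patient-level AUE ANCOVA and listings as supportive. Choose one rule for gaps there, and end the sum at index i+n-1. Carry the method into the Part II SAP.

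The contrasts cost one SAS statement per interval and need no new model; the sensitivity analysis is a modest addition. The drawback is that the main AUE p-value no longer comes from a patient-level ANCOVA.
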